#### **8.5 Histopathology of Excised LN**

The presence of lymphoid tissue for each excised LN will be confirmed by tissue analysis. All LNs will be routinely sectioned and stained with hematoxylin and eosin (H&E). LN ultra-staging will be performed according to the method of Kim et al. Briefly, two adjacent 5- $\mu$ m sections will be cut and sectioned at each of the two levels, 50- $\mu$ m apart from each paraffin block. Sections at each level will be stained with H&E and with immunohistochemistry using anti-cytokeratin AE1:AE3. Image Acquisition and Transmission

Videos of the image sequences acquired using PINPOINT will be recorded to a medical grade video recorder. All required images will be provided to the Sponsor by the Investigative Center.

Image files will be identified using the subject number and initials only (no information identifying the subject shall be included in the files).

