### 10.2 Hypotheses

To assess the effectiveness of PINPOINT in the identification of LNs, a non-inferiority test will be performed using the per-protocol (PP) analysis population.

$$\begin{aligned} H_{01}: \quad p_t &\leq p_c - 0.05 \\ H_{11}: \quad p_t &> p_c - 0.05 \end{aligned}$$

Here  $p_t$  and  $p_c$  represent the effectiveness of LN mapping with PINPOINT and Blue dye respectively. We define the numerator for  $p_t$  as the number of nodes identified with PINPOINT (classifications 1, 3, 5, 7 as defined in section 8.3.1.5) and confirmed as lymphoid tissue, and we define the numerator for  $p_c$  as the number of nodes identified with Blue dye (classifications 2, 3, 6, 7 as defined in section 8.3.1.5) and confirmed as lymphoid tissue. We define the denominator for both  $p_t$  and  $p_c$  as the number of nodes identified by ANY method (classifications 1-7 as defined in section 8.3.1.5). The denominator will include excised nodes confirmed as lymphoid tissue.

A non-inferiority margin of 0.05 was determined to be clinically significant based on feedback from Investigators. Within their respective groups,  $p_t$  and  $p_c$  represent the proportion of LNs identified (and confirmed to be lymphoid tissue, See [Section 8.5](#)) with PINPOINT and Blue dye respectively divided by the total number of LNs identified and excised, across all subjects.

We will repeat the analysis described above using the as-treated (AT) analysis set as a supporting analysis of the primary outcome.

As a sensitivity analysis we will also perform the non-inferiority test using the mITT analysis set. We will also perform sensitivity analyses of the primary endpoint using a best-case and a worst-case scenario. The best-case scenario will consider nodes with missing histology to be lymphoid tissue for PINPOINT and non-lymphoid tissue for Blue dye. The worst case scenario will consider nodes with missing histology to be non-lymphoid tissue for PINPOINT and lymphoid tissue for Blue dye.

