### 10.3 Statistical Analysis

We will use the  $Z_0$  statistic described by Nam and Kwon () in formulae (6) to derive the estimates of  $p_t$ ,  $p_c$ , and the variance of the difference between these estimates to construct the 95% 2-sided confidence interval for  $p_t - p_c$  as:

$$((\hat{p}_t - \hat{p}_c) - 1.96 \times \sqrt{\widehat{var}(\hat{p}_t - \hat{p}_c)} , (\hat{p}_t - \hat{p}_c) + 1.96 \times \sqrt{\widehat{var}(\hat{p}_t - \hat{p}_c)})$$

We will perform this analysis using the PP analysis set to test the inferiority hypothesis ( $H_{01}$ ) stated above, and if the lower bound of the interval is  $> -0.05$  we will claim non-inferiority. If and only if we reject the null ( $H_{01}$ ) hypothesis of inferiority and claim non-inferiority we will use the mITT analysis set to test the null ( $H_{02}$ ) stated below, and if the lower bound of the interval is  $> 0$  we will claim superiority.

$$\begin{aligned} H_{02}: \quad p_t &= p_c \\ H_{12}: \quad p_t &> p_c \end{aligned}$$

We will repeat the analysis described above using the as-treated (AT) analysis set as a supporting analysis of the primary outcome.

As a sensitivity analysis we will also perform the non-inferiority test using the mITT analysis set. We will also perform sensitivity analyses of the primary endpoint using a best-case and a worst-case scenario. The best-case scenario will consider nodes with missing histology to be lymphoid tissue for PINPOINT and non-lymphoid tissue for Blue dye. The worst case scenario will consider nodes with missing histology to be non-lymphoid tissue for PINPOINT and lymphoid tissue for Blue dye.

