This document describes the analyses we will perform in support of the primary study outcome, secondary study outcomes, and safety outcomes. The document includes descriptions of planned analysis sets, planned analyses, and mock-ups of planned tables and listings to display data collected during the study to support the primary and secondary outcomes and the safety outcomes.

We define analysis sets as follows:

Per-protocol (PP)

The Per-Protocol (PP) analysis population includes all subjects that: [1] meet critical eligibility criteria, [2] have no significant protocol deviations; and [3] have evaluable assessment endpoints for the primary endpoint.

We believe that the PP population will be the population that will most likely demonstrate a difference between Blue dye and PINPOINT with respect to their ability to identify LNs, should a difference exist. Thus, since we are trying to show non-inferiority of PINPOINT with respect to Blue dye, we believe that using the PP population for testing non-inferiority is the conservative approach.

Modified Intent to treat (mITT)

The mITT analysis population includes all randomized subjects who received at least one injection of IC2000 or Blue dye. All subjects meeting this criterion are included in the mITT population regardless of whether or not they received the minimally invasive surgical intervention or lymphatic mapping. Subjects who have the mapping procedure aborted due to circumstances such as a higher stage cancer than initially expected will not be included in the mITT. Approximately 8% of subjects are expected to have the mapping procedure aborted.

We believe the mITT population will be the population that will most likely demonstrate no difference between the Blue dye and PINPOINT with respect to their ability to identify LNs, because the mITT population includes subjects who may not have received the full dose of dye, and it includes subjects who may have not received lymphatic mapping, but who may have had LNs identified by gross inspection. Thus, we believe that using the mITT population for testing superiority will be the conservative approach.

As-Treated (AT)

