Following a Blue Duct (Fluorescent Dye Present in Node)						
Confirmed as NOT Lymphatic Tissue						
Confirmed as Lymphatic Tissue						
Confirmed as Lymphatic Tissue (negative for cancer)						
Confirmed as Lymphatic Tissue (positive for cancer)						
Following a Blue and Fluorescent Duct (No Dye Present in Node)						
Confirmed as NOT Lymphatic Tissue						
Confirmed as Lymphatic Tissue						
Confirmed as Lymphatic Tissue (negative for cancer)						
Confirmed as Lymphatic Tissue (positive for cancer)						

Table 3. Lymph Nodes Identified

Identification Method	B-P Arm		P-B Arm		Total	
	N	%	N	%	N	%
Appearance (No Dye Present in Node)						
Confirmed as NOT Lymphatic Tissue						
Confirmed as Lymphatic Tissue						
Confirmed as Lymphatic Tissue (negative for cancer)						
Confirmed as Lymphatic Tissue (positive for cancer)						
Total						
PINPOINT						
Confirmed as NOT Lymphatic Tissue						
Confirmed as Lymphatic Tissue						
Blue Dye						
Confirmed as NOT Lymphatic Tissue						
Confirmed as Lymphatic Tissue						
Neither Dye						
Confirmed as NOT Lymphatic Tissue						
Confirmed as Lymphatic Tissue						
Total						

To assess the effectiveness of PINPOINT in the identification of LNs, a non-inferiority test will be performed using the per-protocol (PP) analysis set.

$$H_{01}: p_t \leq p_c - 0.05$$

$$H_{11}: p_t > p_c - 0.05$$

Here p_t and p_c represent the effectiveness of LN mapping with PINPOINT and Blue dye respectively. We define the numerator for p_t as the number of nodes identified with PINPOINT (i.e., with PINPOINT alone or with both Blue dye and PINPOINT) and confirmed as lymphoid tissue, and we define the numerator for p_c as the number of nodes identified with Blue dye (i.e., with Blue dye alone or with both Blue dye and PINPOINT) and confirmed as lymphoid tissue. We define the denominator for both p_t and p_c as the number of nodes identified by ANY method (i.e., PINPOINT alone, Blue dye alone, both Blue dye and PINPOINT, abnormal appearance or palpably hard, non-stained node found at termination of Fluorescent duct, non-stained node found at termination of Blue duct, non-stained node found at termination of duct stained with both Blue dye and Fluorescent dye). The denominator will include excised nodes confirmed as lymphoid tissue.

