A non-inferiority margin of 0.05 was determined to be clinically significant based on feedback from Investigators. Within their respective groups, p_t and p_c represent the proportion of LNs identified (and confirmed to be lymphoid tissue) with PINPOINT and Blue dye respectively divided by the total number of LNs identified and excised, across all subjects.

We will use the Z_0 statistic described by Nam and Kwon (Nam J-M and Kwon D. Non-inferiority tests for clustered matched-pair data. *Statistics in Medicine*. 2009(28):1668-1679) in formulae (6) to derive the estimates of p_t , p_c , and the variance of the difference between these estimates to construct the 95% 2-sided confidence interval for $p_t - p_c$ as:

$$\left((\hat{p}_t - \hat{p}_c) - 1.96 \times \sqrt{\widehat{var}(\hat{p}_t - \hat{p}_c)} , (\hat{p}_t - \hat{p}_c) + 1.96 \times \sqrt{\widehat{var}(\hat{p}_t - \hat{p}_c)} \right)$$

We will perform this analysis using the PP analysis set to test the inferiority hypothesis (H_{01}) stated above, and if the lower bound of the interval is > -0.05 we will claim non-inferiority. If and only if we reject the null (H_{01}) hypothesis of inferiority and claim non-inferiority we will use the mITT analysis set to test the null hypothesis (H_{02}) stated below, and if the lower bound of the interval is > 0 we will claim superiority.

$$H_{02}: p_t = p_c$$

$$H_{12}: p_t > p_c$$

We will repeat the analysis described above using the as-treated (AT) analysis set as a supporting analysis of the primary outcome.

As a sensitivity analysis we will also perform the non-inferiority test using the mITT analysis set. We will also perform sensitivity analyses of the primary endpoint using a best-case and a worst-case scenario. The best-case scenario will consider nodes with missing histology to be lymphoid tissue for PINPOINT and non-lymphoid tissue for Blue dye. The worst case scenario will consider nodes with missing histology to be non-lymphoid tissue for PINPOINT and lymphoid tissue for Blue dye.

Secondary Efficacy Outcomes

The planned secondary outcomes are intended to support product labelling. We will use the step-down method described by Benjamini and Liu (Benjamini Y, Liu W. A step-down multiple hypothesis testing procedure that controls the false discovery rate under independence. *Journal of Statistical Planning and Inference*. 1999(82):163-170) to control the false discovery rate at 0.05 (2-sided) while testing our secondary objectives.

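### The best- and worst-case rule for missing histology gives a node found by both dyes two tissue states at once, so these sensitivity bounds lie outside anything real histology could show

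*SAP*

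**What the plan says.** Histology is a property of the node. Protocol 8.5 states: "The presence of lymphoid tissue for each excised LN will be confirmed by tissue analysis".

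The primary rates are defined on a shared base. The SAP (Primary Efficacy Outcome) states: "We define the denominator for both p_t and p_c as the number of nodes identified by ANY method". Protocol 10.2 adds: "The denominator will include excised nodes confirmed as lymphoid tissue". A node found by both dyes enters both numerators; for Blue dye the SAP counts nodes found "with Blue dye alone or with both Blue dye and PINPOINT", and the PINPOINT definition mirrors this. Protocol 10.2 also counts class 7 (unstained node at a duct carrying both dyes) in both numerators.

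For missing histology the worst case is: "The worst case scenario will consider nodes with missing histology to be non-lymphoid tissue for PINPOINT and lymphoid tissue for Blue dye". The best case is: "The best-case scenario will consider nodes with missing histology to be lymphoid tissue for PINPOINT and non-lymphoid tissue for Blue dye". The pair appears in Protocol 10.2, 10.3 and 10.7 and in the SAP for the primary outcome, and 10.7 and the SAP extend it to the secondary outcomes. None of these places treats nodes found by both dyes differently, and none says how a missing node enters the denominator.

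**The concern.** A best/worst-case analysis should bracket what the missing results could have shown. This rule assigns tissue status by dye, not by node. For a node found by one dye only, that gives a consistent numerator score. For a node found by both, it makes the same tissue lymphoid for one dye and non-lymphoid for the other, which no pathology result can produce.

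At stake is how the sensitivity analysis reads. The worst case could suggest that a sound non-inferiority result is fragile, and the best case could put the lower limit above 0 where no set of histology results would. Nodes found by both dyes are also the largest class under the planning rates, so this is not a corner case.

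**Working it through.** **Inputs.** From Protocol 10.4: 525 nodes, 84% for PINPOINT, 80% for Blue dye, margin 0.05, ICC at most 0.125, VIF 1.75, effective sample size 300. Assumed, because the documents do not give them: the share of histology missing (m), missing nodes having the planned mix of classes, and missing nodes staying in the common denominator under the rule as written.

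**1. The plan's own figure.** VIF = 1 + (7 − 1) × 0.125 = 1.75; 525/1.75 = 300. SE = √((0.84×0.16 + 0.80×0.20)/300) = 0.0313. Power = Φ(0.09/0.0313 − 1.96) = 0.819, which reproduces the stated 82%.

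**2. One missing node found by both dyes.** If lymphoid, it adds 1 to each numerator and 1 to the denominator. If not, it adds nothing. Either way the numerator difference changes by 0. The rule gives −1 (worst) or +1 (best), that is 1/525 = 0.19 points.

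**3. How many such nodes.** The two rates force the share found by both to lie between 0.84 + 0.80 − 1 = 64% (PINPOINT-only 20%, Blue-only 16%, neither 0%) and 80% (PINPOINT-only 4%, Blue-only 0%, neither 16%).

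**4. Point estimates at m = 5%** (26.25 nodes missing, 498.75 known; known difference 0.04 × 498.75 = 19.95 nodes).

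| | Worst | Best |
|---|---|---|
| Rule as written | (19.95 − 0.80×26.25)/525 = −0.0020 | (19.95 + 0.84×26.25)/525 = +0.0800 |
| Attainable, 64% | (19.95 − 4.2)/519.75 = +0.0303 | (19.95 + 5.25)/504 = +0.0500 |
| Attainable, 80% | 19.95/523.95 = +0.0381 | 21/499.8 = +0.0420 |

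At 64%, 16.8 of the missing nodes are found by both, and 16.8/525 = 3.2 points, which is the gap in the worst case.

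**5. Where the worst-case lower limit reaches −0.05.** With the planning SE this happens when the difference falls to 1.96 × 0.0313 − 0.05 = 0.0114.
- Rule: 0.04 − 0.84m = 0.0114, so m = 3.4% (18 nodes).
- Attainable, 64%: (0.04 − 0.20m)/(1 − 0.20m) = 0.0114, so m = 14.5%.

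The planned interval is for matched pairs, so I repeated this with SE = √(VIF × ((P + B)/n − d²)/n), where P and B are the nodes counted for PINPOINT only and for Blue dye only, n is the denominator and d = (P − B)/n. With VIF 1.75:
- Rule, 64%: m = 2.5% (13 nodes). P = 102.4, B = 81.9 + 10.5 = 92.4, d = 0.0190, SE = 0.0351, limit −0.050.
- Rule, 80%: m = 6.7% (35 nodes). P = 19.6, B = 28.1, d = −0.0163, SE = 0.0174, limit −0.050.
- Attainable: m = 9.9% at 64%; no crossing up to 90% missing at 80%.

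**6. Low missing rates.** At 1% and 2% missing the rule's worst-case limit is −0.030 and −0.038 (planning SE), or −0.037 and −0.045 (paired, 64%). The margin is not crossed.

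**7. Best case at 5%, paired SE, VIF 1.75.** At 64%: rule P = 121.8, B = 79.8, d = 0.0800, SE = 0.0355, limit +0.010. The highest attainable limit is −0.019 (P = 105, B = 79.8, n = 520.8). At 80%, the limit with complete data is 0.04 − 1.96 × 0.0113 = +0.018, already above 0.

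**The case against.** **The worst case is conservative.** Under the common denominator it is harsher to PINPOINT than any real histology, so a non-inferiority result that survives it survives everything attainable. No claim depends on either scenario; the claims rest on the PP and mITT intervals. This stands, and it limits the point to the sensitivity analyses.

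**Missing histology may be rare.** Every excised node is to be examined, and the per-protocol set requires that subjects "have evaluable assessment endpoints for the primary endpoint". This stands in part: that condition applies to subjects, not to single nodes, and the mITT set has no such condition. At 1% to 2% missing, the margin is not crossed.

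**The figures depend on the overlap, the variance and the rates.** This stands. The 64% share needs every node to be found by at least one dye, yet class 4 nodes count for neither. At 80% and 5% missing the rule's worst-case limit is −0.034, so nothing is lost at that rate. Applying VIF 1.75 to a paired variance is debatable; with VIF 1 + (3.5 − 1) × 0.125 = 1.31 the rule crosses at 3.6% (64%) to 7.1% (80%). At the literature average of 91% and 80% it crosses only at 10.3% to 12.1% (paired, VIF 1.75).

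**Stronger readings the documents do not support.** The SAP wording "Within their respective groups, p_t and p_c represent the proportion of LNs identified" might suggest a separate denominator for each dye, which would make the worst case too lenient. The same sentence goes on to divide by a single total over all subjects, and the preceding definition sets one denominator for both rates. A reader might also infer that the best case generally creates a false superiority signal. It can at 64%, but at 80% the lower limit is above 0 with nothing missing, so no verdict changes.

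**Conclusion.** The rule is wrong as written, for the sensitivity analyses only. It gives a missing node found by both dyes a state that cannot occur, and its bounds leave the attainable range by about 0.19 points per such node. At an assumed 5% missing that is roughly 3 to 4 points on each side, against a 5-point margin.

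The worst case is over-strict but remains a valid outer bound. It can show non-inferiority as lost from about 2.5% to 6.7% missing (paired SE, VIF 1.75) or 3.4% (planning SE). The best case is over-favourable, and changes the reading only towards the 64% end of the overlap. These sizes rest on the planning rates, an assumed missing rate and missing nodes that resemble the rest. The primary test, its power and the claim rules are unaffected. The same inconsistency carries over to the secondary outcomes, where I have not calculated its size.

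**What to change.** In Protocol 10.2, 10.3 and 10.7 and in the SAP, give each missing-histology node one tissue state that holds for both dyes, with the common denominator following it:

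- Lymphoid: the node is in the denominator and in the numerator of every method that found it.
- Non-lymphoid: the node is in neither.
- Worst case: PINPOINT-only nodes non-lymphoid, Blue-only nodes lymphoid. Best case: the reverse.
- Nodes found by both dyes or by neither take one common state, with each scenario run both ways. This moves only the denominator: at 5% missing and 64% overlap the worst-case limit is −0.037 or −0.038.

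Apply the same rule to the secondary outcomes. Report the number of missing-histology nodes by class, since SAP Table 3 has no row for them. The cost is a few sentences and a little programming; no additional data are needed.
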